### 15.3. Data Analysis

#### 15.3.1. Subject Disposition

The number and percentage of subjects screened, screen failed, enrolled, dosed, and completing the study will be summarized. The number and percentage of subjects who terminate early will also be summarized, with reasons for early termination.

### **15.3.2. Drug Exposure and Compliance**

A data listing, by subject, containing the study medication dosing and dosing errors, if any, will be provided. Treatment compliance will not be summarized as all dosing will occur in-clinic.

The total number of days of exposure will be summarized categorically (N [%]).

### **15.3.3. Important Protocol Deviations**

Important protocol deviations (IPDs) will be identified and documented based on a review of potential IPDs. The potential IPDs will be identified through programmatic checks of study data, as well as through review of selected data listings. The potential IPDs to be reviewed include, but are not limited to, subjects who:

- Did not meet inclusion/exclusion criteria.
- Received any disallowed concomitant medication.

Individual IPDs will be presented in a data listing. The number and percentage of subjects with IPDs will be summarized by type of deviation and dose group.

### **15.3.4. Demographic and Baseline Characteristics**

Basic demographics (e.g. age, gender, race, ethnicity, etc.) will be summarized descriptively. Medical history will be coded using MedDRA, and will be summarized for the safety population by presenting the number and percentage of subjects with at least one condition in each system organ class (SOC) and preferred term (PT).

### **15.3.5. Medical History and Psychiatric History**

Medical and psychiatric history will be coded using MedDRA. The count and percentage of subjects under each history term, coded by SOC and PT, will be summarized.

### **15.3.6. Positron Emission Tomography (PET) and Functional Magnetic Resonance Imaging (fMRI) Analysis**

The analysis of brain dopamine synthesis capacity and fMRI analysis will use the PET population.

The region of interest in the primary endpoint is the whole striatum. Exploratory analyses will be conducted in other regions and sub-regions of interest. The cerebellum will be used as the reference region. The regions of interest will be delineated on the subjects structural MR based on using the Hammersmith Atlas, and this will be co-registered to the subject's dynamic PET images. Dopamine synthesis capacity will be calculated based on each individual PET images collected at each scan for each subject using a Patlak Graphical Analysis. For the fMRI image pre-processing will be performed via the CONN toolbox (version 17.b)(65) for Statistical Parametric Mapping software (SPM 12 (6906)). For each participant, BOLD signal time-series will be extracted from the nodes in the Gordon cortical atlas, and functional connectivity determined within primary networks of interest (the default mode network, the salience network) and the visual network (a control network), and additional networks guided by the PET analysis.

The primary endpoint is the change from baseline in dopamine synthesis capacity at Week 2 will be calculated, together with 95% confidence interval from a paired sample t distribution.

Changes in resting state BOLD fMRI signal within the salience, default mode, and visual networks at each post-dose time point from baseline will be summarized.

Changes in exploratory MRI markers, including (but not limited to) neuromelanin and iron signal at each post-dose time point from baseline will be summarized.

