#### **Statistical Methods:**

**PET Analysis:** The region of interest in the primary endpoint is the whole striatum. Exploratory analyses will be conducted in other regions and sub-regions of interest. The cerebellum will be used

as the reference region. Dopamine synthesis capacity will be calculated based on each individual PET images collected at each scan for each subject.

**Statistical Analysis:** The analysis of brain dopamine synthesis capacity and fMRI analysis will use the PET population, which include subjects who were administered at least one dose of SEP-363856 and have a baseline and a post-baseline PET assessment. The change from baseline in dopamine synthesis capacity at Week 2 will be calculated, together with 95% confidence interval from a paired sample t distribution. Changes in resting state BOLD fMRI signal at each post-dose time point from baseline will be summarized. Changes in exploratory MRI markers, including (but not limited to) neuromelanin and iron signal at each post-dose time point from baseline will be summarized. The efficacy population will include all subjects who have received at least one dose of SEP-363856, and have any postdose data for the PANSS, CGI-S, BNSS or MADRS. Efficacy data will be based on this population. Changes from baseline at each post-dose time point will be summarized, with 95% confidence intervals.

Safety analyses will use the Safety population, which includes all subjects who have received at least one dose of study drug. Safety measures will be summarized descriptively.

Treatment emergent adverse events (TEAEs) will be summarized by presenting the number and percentage of subjects with any TEAEs, and AEs by system organ class and preferred term. Adverse events will be further summarized by severity and by relationship to study drug. The summary of TEAEs will be limited to events occurring on or after the first dose of study drug. All AEs, as well as a listing of deaths, SAEs, or AEs leading to discontinuation, will be presented in listings.

Vital signs, ECG parameters, and laboratory data will be summarized by presenting summary statistics of actual values and change from baseline values. The number and percentage of subjects with potentially clinically significant post-baseline values for selected parameters will be presented. The incidence of orthostatic hypotension and orthostatic tachycardia will be summarized.

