j Blood samples for antipsychotic plasma concentrations will be collected at Screening, Day -2, Day 1 (approximately 10 minutes prior to dosing), Day 2 (2 - 4 hours postdose), Day 7 (2 – 4 hours postdose), Day 14 (prior to PET scan), and at Follow-up.

k Additional urine drug screen may be ordered as deemed clinically appropriate. These results should be discussed with the Medical Monitor.

l Each PET scan will be accompanied by intravenous administration of radiotracer  $^{18}\text{F}$ -DOPA and oral pre-treatment (1 hour prior to tracer) with 150 mg carbidopa and 400 mg entacapone. If PET/MR scanner is unavailable for technical reasons separate PET and MR scans (on an alternate PET scanner without MR and alternate MR scanner) will be permitted. Prior to each PET scan, there is a period of resting state fMRI collection. In addition to fMRI scan sequences, exploratory MRI sequences may be performed during each of the MRI and PET/MR acquisition times and may include (but not limited to) a neuromelanin-sensitive MRI (NM-MRI) sequence and an iron-sensitive MRI sequence (effective transverse relaxation rate [R2\*] or Quantitative Susceptibility Mapping [QSM]). Repeat MRI including exploratory MRI sequences may be performed where it is not possible to obtain complete measures during the PET-MRI scan.

m In the event of unsuccessful PET scan on Day 14, additional days of dosing may be necessary up to, but not exceeding, Day 19. If any such additional days are necessary, subjects will continue their usual daily dosing. PANSS, BNSS, MADRS, and CGI-S may be assessed  $\pm 1$  day of PET scan; other assessments are to be completed the same day as the PET scan. Participants will only receive 3 PET scans in the event that a scan is not able to be completed or is not suitable for analysis. It is expected that the majority of participants will receive up to 2 PET scans which would result in an effective dose of 7.4 mSv.

n PET scan to be performed at early termination (ET) visit only if the subject terminates the study prior to Day 14 PET scan.

o Only perform PANSS, BNSS, CGI-S, and MADRS if subject discontinues prior to Day 14 scan day.

p At the screening visit, the “Baseline/Screening” version will be completed; the “Since Last Visit” version of the C-SSRS will be administered for all other visits. C-SSRS should be performed prior to PET scan on Day 14.

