### 11.4. PET/fMRI Assessments

It is important that the participant is examined under the same conditions at baseline and subsequent scan, including scanning at the same time of day where possible (scanning time of day should be  $\pm$  3h from the time of day of the baseline scan where possible), and head motion monitored and minimised. The post-dose scan should be timed to occur so that the start is approximately at the time in which maximum observed plasma concentration ( $C_{max}$ ) occurs. Post dose fMRI scanning will start approximately 2 to 4 hours after dosing.

Prior to entry into the scanner, subjects will complete the site's standard radiography screening questionnaire to ensure they are safe to enter the scanner environment (eg, no history of surgery involving metal implants). Females will undergo urine pregnancy test to exclude pregnancy. Scan date as well as start and stop time will be collected.

Approximately 1 hour before the scan participants will receive 150 mg of carbidopa and 400 mg of entacapone orally. This inhibits the formation of radiolabeled metabolites of F-DOPA that may cross the blood-brain barrier, and boosts the signal to noise ratio. Subjects will have an IV canula placed in the ante-cubital fossa for administration of F-DOPA. Prior to scanning they will be asked to go to the toilet.

Striatal dopamine synthesis capacity (DSC) assessment ( $K_i$ ) using  $^{18}\text{F}$ -DOPA kinetic analysis will be performed.

In addition to fMRI scan sequences, exploratory MRI sequences may be performed during each of the MRI and PET/MR acquisition times and may include (but not limited to) a neuromelanin-sensitive MRI (NM-MRI) sequence and an iron-sensitive MRI sequence (effective transverse relaxation rate [ $R_2^*$ ] or Quantitative Susceptibility Mapping [QSM]). Repeat MRI including exploratory MRI sequences may be performed where it is not possible to obtain complete measures during the PET-MRI scan.

The majority of participants will receive up to 2 PET scans. Participants will only receive 3 PET scans in the event that a scan is not able to be completed or is not suitable for analysis.

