### 15.2. Analysis Populations

The following populations will be defined:

- Safety Population: The safety population will consist of all subjects who receive at least one dose of study drug.
- PET Population: The PET population is defined as all subjects who took at least one dose of SEP-363856 and have a baseline and a post-baseline PET assessment.
- Efficacy population: the efficacy population is defined as all subjects who have received at least one dose of study drug, and have any postdose data for the PANSS, CGI-S, BNSS or MADRS.
- Per Protocol Population: The Per Protocol Population is defined as all subjects in the PET population, the subject completed the study, and the subject had NO important protocol deviations.

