### 6. ANALYSIS POPULATIONS

Enrolled subjects are subjects who signed the ICF and did not screen fail at their final screening.

Three analysis populations will be defined in this study. The population for PET and fMRI analyses will be specified in a separate Statistical Analysis Plan.

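### Resting-state fMRI change is analysed only in subjects with paired PET, so a usable fMRI pair is excluded when the post-baseline PET is missing; the exploratory MRI markers have no stated population

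*Protocol*

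**What the plan says.** The synopsis (Statistical Methods) and protocol 15.3.6 assign one population to two kinds of measurement: "The analysis of brain dopamine synthesis capacity and fMRI analysis will use the PET population". Section 15.2 defines it as subjects who took study drug and "have a baseline and a post-baseline PET assessment". The definition sets no MRI condition and does not say whether an assessment must be evaluable or merely performed. Section 15.2 defines no MRI or fMRI population, although section 6.3 lists fMRI change at Week 2 as an endpoint.

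For the other MR measures, 15.3.6 says: "Changes in exploratory MRI markers, including (but not limited to) neuromelanin and iron signal at each post-dose time point from baseline will be summarized". That sentence names no population.

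On acquisition, Table 2 footnote l says: "Prior to each PET scan, there is a period of resting state fMRI collection". It also permits separate machines: "If PET/MR scanner is unavailable for technical reasons separate PET and MR scans" may be used. MRI may be repeated where the MR measures were incomplete. On failed PET, section 11.4 says: "Participants will only receive 3 PET scans in the event that a scan is not able to be completed or is not suitable for analysis".

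The SAP (section 5.3) takes PET and fMRI out of its scope, and section 6 adds: "The population for PET and fMRI analyses will be specified in a separate Statistical Analysis Plan". That plan is not among the documents.

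**The concern.** The analysis set for an endpoint should depend on whether that endpoint was validly measured. Here, entry to the fMRI analysis depends on a different modality. Under the protocol, fMRI comes before PET, and it may be acquired on another scanner. A subject can therefore complete usable fMRI at both visits and still lack a post-baseline PET assessment. That subject's fMRI pair would be left out, and since section 15.3.11 rules out imputation, nothing would replace it.

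The mismatch also runs the other way. Because the PET population has no MRI condition, it can include subjects with no usable fMRI pair, so it does not give the correct fMRI denominator either.

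At stake is precision for an exploratory endpoint in a study of 22 subjects, where each pair counts. The exploratory MRI markers have a related but different gap: a reader cannot tell from the protocol which subjects they cover.

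**Working it through.** **The plan's own figure.** Protocol 15.1 claims more than 90% power with 16 PET pairs for a reduction of 0.0005/min, with SD 0.00056/min and alpha 0.05. Treating 0.00056 as the SD of the change, the noncentrality is 0.0005 / (0.00056/√16) = 3.57 on 15 df, and the exact two-sided power is 91.5%. For the total, 16 / (1 − 0.25) = 21.3, rounded up to 22. Both figures reproduce. They concern PET only; the documents state no sample size or power for fMRI.

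**Who is excluded.** Reading 15.3.6 with 15.2, for a dosed subject with a baseline PET:

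| Post-baseline fMRI | Post-baseline PET assessment | In the fMRI analysis set? |
|---|---|---|
| usable | present | yes |
| usable | absent | no: a valid pair is lost |
| not usable | present | in the set, but contributes no fMRI change |
| not usable | absent | no: nothing is lost |

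Only the second row is a loss. Baseline failures matter less, because the screening scan precedes dosing and subjects who fail screening on imaging results are not dosed.

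**How many.** Inputs from 15.1: 22 subjects in total and at least 16 with complete PET. If the floor of 16 is met and all 22 are dosed, 22 − 16 = 6 subjects lack paired PET, and 6/22 = 27%. The number of these six with paired fMRI is not given, so the range is 0 to 6.

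**Effect on precision.** For a mean paired change, the 95% half-width in units of the SD of the change is t(0.975, n−1)/√n. The last column takes 16 PET pairs as the restricted set.

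| fMRI pairs if PET is not required | Half-width (SD) | Restricted interval wider by |
|---|---|---|
| 16 (no PET-only loss) | 0.533 | 0% |
| 18 | 0.497 | 0.533/0.497 − 1 = 7% |
| 20 | 0.468 | 0.533/0.468 − 1 = 14% |
| 22 (all six recoverable) | 0.443 | 0.533/0.443 − 1 = 20% |

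The rows for 18 and 20 are illustrations within the range, not estimates. The protocol attaches a 95% interval only to the primary PET change and says the fMRI change will be summarised, so these widths apply to any interval that is reported for fMRI.

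**The case against.** The strongest reply is that the loss may be nil.

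- **Repeats.** A failed PET can be repeated: a third scan is foreseen and dosing may run to Day 19. This stands, and it rules out inferring that every failed PET costs an fMRI pair. It does not close the gap, because three scans in total and Day 19 are the limits.
- **Shared session.** PET and MR are normally one session, also at early termination, so a drop-out without a second PET usually has no second fMRI. This stands and pulls the figure towards zero. A reader might take the 25% in 15.1 as a PET-only failure rate; it is drop-out, and the documents do not support treating it as recoverable fMRI.
- **Timing.** SAP 4.1 places fMRI during the PET scan, in two periods, whereas the protocol places it before. If the SAP is right, an aborted session could lose both measures. The documents need to agree on this.
- **MRI markers.** A reader might infer that neuromelanin and iron are also confined to the PET population, since they sit in the same section. The rule names only dopamine synthesis capacity and fMRI, so the marker population is unstated, not restricted.
- **Common set.** Additional fMRI networks are to be guided by the PET analysis, and one objective relates MRI markers to PET. That supports using subjects with both measures for the relationship analyses. It does not justify requiring PET for the stand-alone fMRI change.
- **Separate plan.** The imaging SAP may already define another population. This cannot be checked. The SAP's list of changes from the protocol (section 4.2) records none for fMRI, so the protocol rule is the only one visible.

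**Conclusion.** The point holds for resting-state fMRI. As written, the protocol excludes a dosed subject with a usable fMRI pair when there is no post-baseline PET assessment. For the exploratory MRI markers the finding is only that no population is stated.

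The size is 0 to at most 6 of 22 subjects, and 0% to at most 20% on the width of any 95% interval for the fMRI change. The upper end assumes that all 22 subjects are dosed, that PET pairs stop at the planned floor of 16, and that every subject without paired PET has two usable fMRI sessions. Nothing in the documents supports that last condition, so the 20% is a bound and not an expectation; the true figure is probably near the low end.

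A reader might infer that the trial's main result is weakened. It is not: the endpoints concerned are non-primary and descriptive, and the 91.5% power for the primary PET analysis does not change. The conclusion also depends on the separate imaging SAP not having already replaced the rule. The point is modest, but worth acting on because the change costs almost nothing and can only keep or add valid pairs.

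**What to change.** In protocol 15.2, 15.3.6, the matching synopsis text and the imaging SAP:

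1. Define the set for fMRI, and for each MRI marker separately, as dosed subjects with usable baseline and post-baseline data for that measure, whether or not PET is available.
2. Keep the PET population for dopamine synthesis capacity, and state whether a PET assessment must be evaluable to count.
3. Use subjects with both measures only for analyses that relate MRI to PET.
4. Reconcile the protocol and SAP 4.1 on whether fMRI is collected before or during the PET scan.

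If the imaging SAP already does this, a cross-reference and an aligned protocol sentence are enough. The cost is wording only, with no new procedures or scans. The one downside is that n will differ between the PET and MRI tables, so each table should show its own n.

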### **15.3.7. Efficacy Analyses**

Efficacy parameters include PANSS, CGI-S, BNSS, and MADRS. Tabular and graphical summaries will be based on the Efficacy Population.

The actual and changes from baseline at each post-dose time point will be summarized, with 95% confidence intervals. The relationship between dopamine synthesis capacity at baseline and measures of baseline symptom severity (PANSS, CGI-S, BNSS, and MADRS) and their change from baseline will be presented graphically.

#### **15.3.7.1. Subgroup Analysis**

Subgroup analyses are not planned for the efficacy parameters.

### **15.3.8. Safety Analyses**

#### **15.3.8.1. Adverse Events**

All AEs will be coded using MedDRA.

Treatment emergent AEs (TEAEs) are untoward medical occurrences:

- that occurred on or after the first dose of study medication,
- with a missing start date and a stop date on or after the first dose of study medication, or
- with both a missing start and stop date.

TEAEs will be summarized by MedDRA system organ class (SOC) and Preferred Term (PT).

The following TEAEs will be summarized and presented by MedDRA SOC and PT for the Safety population:

- All TEAEs (including number of events and subject incidence).
- TEAEs by severity (mild, moderate, severe).
- TEAEs by relationship to the study treatment (related, or not related).

The following conventions will be followed in summarizing TEAEs:

- For subject incidence summaries, each subject will be counted only once within each SOC and within each preferred term.
- If a subject reports more than one TEAE within a preferred term and/or a body system, the AE with the highest known severity within each body system and within each preferred term will be included in the summaries by severity.

- For summaries by relationship to the study medication, TEAEs will be grouped as “related” or “not related.” TEAEs assessed as “possible,” “probable,” or “definite,” will be grouped as “related.” If a subject reports more than one TEAE within the same treatment regimen, SOC and PT, and any are related, it will be summarized as related.

Untoward medical occurrences that occur between the time of signing the ICF and first drug administration are pretreatment events.

A listing of all AEs, as well as a listing of deaths, SAEs, or AEs leading to discontinuation, will be presented.

#### **15.3.8.2. Clinical Laboratory Assessments**

Laboratory data will be summarized overall for the safety population.

For laboratory parameters with continuous outcomes, descriptive statistics (number of subjects, mean, SD, median, minimum, and maximum) for the observed values and for changes from baseline will be presented and overall at each visit. For laboratory parameters with categorical outcomes, the number and percentage of subjects with each outcome will be presented for each dose cohort and overall at each visit.

The number and percentage of subjects with Sponsor defined potentially clinically significant (PCS) laboratory values (defined in the SAP) will be summarized for each dose cohort and overall at each visit. The data listings for laboratory parameters will flag values outside of the reference range. Clinically significant laboratory findings will be displayed in a separate data listing.

#### **15.3.8.3. Electrocardiograms**

Electrocardiogram parameters to be collected include ventricular heart rate, QT interval, PR interval, QRS duration, and RR interval (ms). The corrected QT interval will be derived according to the Fridericia formula (QTcF) as well as Bazett’s formula (QTcB).

ECG data will be summarized overall for the safety population.

Electrocardiogram parameters and changes in these parameters from baseline, as determined by the central over-read, will be summarized using descriptive statistics (number of subjects, mean, standard deviation, median, minimum, and maximum) at each visit.

The number and percentage of subjects with QTcF values in the following categories will be summarized:

- QTcF  $\geq$  500 ms at any postdose timepoint and not present at baseline.
- QTcF  $\geq$  480 ms at any postdose time point and not present at baseline.
- QTcF  $\geq$  450 ms at any postdose timepoint and not present at baseline.
- Change from baseline in QTcF  $\geq$  60 ms for at least one postdose measurement.
- Change from baseline in QTcF  $\geq$  30 ms for at least one postdose measurement, but  $\leq$  60 ms for all postdose measurements.

For these categorical analyses, the percent of subjects will be based on the number of subjects with at least one non-missing post treatment value. Any early termination visit or unscheduled ECG that occurs after the single dose will be included for these posttreatment summaries.

The number and percentage of subjects with potentially clinically significant post-baseline values (defined in the SAP) will be presented.

